participants so far. Follow-up counseling/referral phone calls were successfully placed for all detected openings and only four were not reached within 24 hours. All participants successfully reached for follow-up reported having taken the test **minutes** after opening it, suggesting that monitoring the kit's **opening** serves as a reasonable marker of when they **took** the test. Figure 3 shows study outcomes to date. These data show that 96% of those in the eTEST group have tested for HIV at some time during the study period, compared with 90% for standard HBST, and 62% for control. Among the 63% of participants who have completed Month 5 of the study, repeat testing rates (reporting testing during **both** of the first two 3-month periods) were 92% in eTEST, 54% in standard HBST, and 46% in control. Rates of testing for other STIs were modestly higher in the HBST conditions, but this difference is difficult to interpret due to the small sample size and may not be meaningful.

Over 72% of eTEST participants received risk reduction counseling during the study period (control=18%, standard HBST=15%). While PrEP was not an explicit focus of the follow-up phone calls, 25% of eTEST participants reported having consulted with a physician about PrEP and 10% reported having started PrEP as a result, compared with 4% who sought consultation and started PrEP in the control group. While AA and H/L participants comprised only 21% of this sample, over 75% of those assigned to HBST conditions tested for HIV at some point during the study period, compared with 43% in the control condition. Moreover, 67% reported testing during both the first two quarters of the study so far, compared with 33% in the control condition.

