**Power Considerations.** We used past studies and power estimation/ simulation packages in *R*, to determine the sample sizes necessary to detect significant effects in each of the models proposed in 3C.3.8. Relative risk ratios (RRs) were estimated for relevant outcomes (e.g., HIV testing, STI testing) across study conditions in our pilot data, and we used the smallest of these group differences for estimation so as to provide the most conservative estimate of required sample size. For each estimate, we assumed  $\alpha=0.05$ , an observed power of .80, and a small but constant effect (1.2) for study site on each outcome, to ensure that any differences emerging between study sites could be detected. For GEE models, we assumed quarterly measurements ( $T = 4$ ), with relatively independent relationships between repeated data ( $\Phi=0.2$ ). Table 2 summarizes the models, outcomes, parameters, and sample size estimates for each aim. For GEEs, sample size gives the estimated number of participants needed to test condition effects within each site. The sample size required to detect the most complex model with the smallest effects is 246. To account for missing data, we propose collecting 300 MSM at each site.

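### The stated 246 per site does not give 80% power for the smallest HIV-testing differences that the pilot reports, so the conservative label fails and within-site power is overstated

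*Combined protocol and SAP*

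**What the plan says.** The Power Considerations paragraph in B.4 says of the pilot risk ratios that "we used the smallest of these group differences for estimation so as to provide the most conservative estimate of required sample size". It assumes alpha of 0.05, "an observed power of .80, and a small but constant effect (1.2) for study site on each outcome". For the GEE models it takes four quarterly measurements "with relatively independent relationships between repeated data", with a coefficient of 0.2. The GEE sample size is described as the number needed to test condition within each site. The result is: "The sample size required to detect the most complex model with the smallest effects is 246". The paragraph then proposes 300 per site to allow for missing data.

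Planned Analyses counts 300 as 54 per site, 162 in total, above the requirement. It relies on that surplus to say the most complex model will be fully powered even if many participants start PrEP.

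The pilot results in B.1 report that "96% of those in the eTEST group have tested for HIV at some time during the study period, compared with 90% for standard HBST", with 62% in control. Rates of testing in both of the first two quarters "were 92% in eTEST, 54% in standard HBST, and 46% in control". Risk reduction counseling was 72% in eTEST, 18% in control and 15% in standard HBST.

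The Overview of Research in B.1 sets enrolment at 2000, 666 per metro, and promises efficacy analyses within and across regions.

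**The concern.** A sample size built on the smallest pilot difference should give at least 80% power for every difference the pilot reports. Two of the reported HIV-testing differences are only 6 and 8 percentage points, and 82 per arm looks too few for either.

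The plan relies on 246 in two ways. It is the basis for claiming condition can be tested within each site, and it supplies the margin said to absorb PrEP uptake. If the figure does not hold, a null within-site comparison of eTEST with standard HBST could be read as evidence of no benefit when the test had little chance of finding one. eTEST against standard HBST is a named Aim 1 comparison.

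**Working it through.** **Inputs.** Alpha 0.05, power 0.80, T = 4 and phi = 0.2 come from Power Considerations; pilot rates come from B.1. Two assumptions are mine, because the text does not state them: a two-sided test and 1:1:1 allocation. The site effect of 1.2 is not modelled, and there is no allowance for missing data or multiple comparisons.

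**Unit of 246.** 300 − 246 = 54 and 3 × 54 = 162, matching Planned Analyses, so the plan reads 246 as per site. That is 246 / 3 = 82 per arm within a site, or 246 per arm pooled over three sites. Likewise 300 per site is 100 per arm, 666 per site is 222 per arm, and 2000 in total is 667 per arm.

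**Formulas.** With p̄ = (p1 + p2)/2:

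- n per arm, single binary outcome = [1.960·√(2p̄(1−p̄)) + 0.842·√(p1(1−p1) + p2(1−p2))]² / (p1−p2)²
- four-quarter GEE: multiply n by (1 + 3·phi)/4, which is 0.40 at phi = 0.2
- power = Φ{[|p1−p2|·√m − 1.960·√(2p̄(1−p̄))] / √(p1(1−p1) + p2(1−p2))}, where m is n per arm for a single outcome and n/0.40 for the GEE

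**Trying to reproduce 246.** Table 2, which holds the plan's risk ratios, is not in the available text, so its calculation cannot be rerun. Read per site over three arms, none of the small contrasts tabulated below gives 246. One gives nearly that number per arm: 54% against 46% needs 612.0 × 0.40 = 244.8, so 245 per arm, or 3 × 245 = 735 per site.

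**96% against 90%.** Planned Analyses tests any HIV test by logistic regression, so the single-outcome formula applies: n = (0.707 + 0.302)² / 0.06² ≈ 283 per arm. At 82 per arm, power = Φ[(0.543 − 0.707)/0.358] = Φ(−0.457) = 32%.

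**54% against 46%, taken as a quarterly rate.** At 82 per arm, m = 82/0.40 = 205 and power = Φ[(1.145 − 1.386)/0.705] = Φ(−0.341) = 37%.

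| Contrast | Model | n per arm for 80% | 82/arm (246 per site) | 100/arm (300 per site) | 222/arm (666 per site) | 246/arm (pooled, 246 per site) | 667/arm (pooled, 2000) |
|---|---|---|---|---|---|---|---|
| 96% v 90%, any test, eTEST v standard | single outcome | 283 | 32% | 38% | 70% | 74% | 99% |
| 54% v 46%, standard v control | GEE, phi 0.2 | 245 | 37% | 43% | 76% | 80% | >99% |
| 18% v 15%, counseling, control v standard | GEE, phi 0.2 | 961 | 13% | 15% | 27% | 29% | 65% |

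Treating 96% against 90% as a four-quarter GEE at phi = 0.2 gives 66% at 82 per arm, still below 80%. Large eTEST contrasts, such as 92% against 54% and 72% against 15%, exceed 99% power at 82 per arm.

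**Sensitivity to phi.** For 54% against 46% at 222 per arm, power is 84% at phi 0.1, 76% at 0.2, 69% at 0.3 and 48% at 0.7. Pooled at 667 per arm it is still 91% at phi 0.7.

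**The case against.** **The GEE outcome is testing in each quarter, and the 54% and 46% are rates of testing in both of two quarters.** This is the strongest point. Averaging the any-test and both-quarters rates gives implied quarterly rates of (96+92)/2 = 94%, (90+54)/2 = 72% and (62+46)/2 = 54%. At 82 per arm and phi = 0.2, power is then 97% for 72% against 54% and above 99% for 94% against 72%. So the HIV-testing GEE may be adequately powered at 246 per site. But the averaging mixes denominators: any-test rates cover participants to date, while both-quarters rates cover only the 63% who had completed Month 5. The 54% against 46% result therefore depends on how the rate is used. The 96% against 90% result does not.

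**The small contrasts are not what the within-site sentence covers.** The any-test model is a logistic regression, not a GEE, and 54% against 46% does not involve eTEST, whereas Aim 1 tests eTEST against each comparator. Both statements are true. Even so, 96% against 90% is an Aim 1 contrast, the paragraph claims the smallest pilot difference, and the plan promises within-region efficacy.

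**Stronger readings that the documents do not support.**

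- A reader might infer that the plan ignored its smallest differences. Without Table 2 this cannot be shown, and the match at 245 per arm suggests that 54% against 46% may have been used.
- A reader might put 54% against 46% into the single-outcome formula, giving 612 per arm and 39% power at 222 per arm. That drops the repeated measurements on which the plan's model for regular testing rests.
- A reader might infer that the pilot contradicts phi = 0.2. Combining the any and both rates gives 0.65, 0.11 and 0.68 by arm, mean 0.48, but with the same mixed denominators. Raising the any rates by 4 points (capped at 100%) brings the mean to 0.17. In a simulation with a true value of 0.2 and 15 to 24 per arm, this mean ranged from about −0.16 to 0.82 (95% range).

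**Conclusion.** The point holds in a limited form. Read per site, as the plan reads it, 246 does not give 80% power for the small HIV-testing differences in B.1: 32% for 96% against 90%, and 37% for 54% against 46% if that is taken as a quarterly rate. The description of the estimate as the most conservative is not supported. At 666 per site, within-site power is about 70% and 76%, still short.

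A reader might infer that the trial as a whole is underpowered. It is not, for HIV testing: pooled at 2000, both contrasts reach about 99% or more. Counseling at 18% against 15% would have 65% even pooled, but it compares standard HBST with control.

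That a per-arm number was used as a per-site number is plausible but unproven. If it was, the requirement would be about 735 per site, above both 300 and 666.

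The conclusion assumes two-sided testing and equal allocation, and takes the pilot rates at face value although they come from 73 participants.

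**What to change.** 1. State whether 246 is per arm or per site, and show the rates, risk ratio and model behind it.
2. Recompute the power table with the B.1 differences at the actual enrolment. Use the single-outcome formula for the any-test logistic model and the factor (1 + 3·phi)/4 for quarterly outcomes. State the assumed quarterly rates rather than borrowing the both-quarters rates without comment. Show a range of phi, for example 0.1 to 0.7, as a sensitivity analysis only.
3. Remove the conservative and fully powered claims where they do not hold, including the argument that the 54-per-site surplus covers PrEP uptake.
4. Claim 80% power for the pooled HIV-testing contrasts. Report within-site power of about 70% to 76% for the small HIV-testing contrasts and label those comparisons as descriptive.

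The cost is a recalculation and restated figures, with no extra participants. The downside is that the stated within-site power becomes less favourable.

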**Overview of Research.** Given these issues, the proposed research involves conducting a fully-powered efficacy test of HBST and the eTEST system's effects on rates of any/repeat HIV testing, use of other prevention services (e.g., STI testing, HIV risk reduction counseling), and PrEP linkage/initiation, compared with "standard" HBST and reminders for clinic-based testing, among high-risk MSM in three regions in the US: The Deep South (Jackson, MS), West Coast (Los Angeles), and Northeast (Providence/Boston). High-risk MSM ( $N=2000$ ,  $N=666$  per metro) who have not tested in the last year will be recruited online using an interactive web application. Participants will be randomly assigned to one of three arms that involve receiving one of the following at baseline, 3, 6, and 9 months: (1) HBST with phone follow-up (eTEST condition), (2) standard HBST (no follow-up), or (3) reminders for clinic-based testing only (control). Only enhanced eTest participants will be provided with the eTEST app, which will monitor the status of HBST kits and facilitate phone follow-up. Control participants will receive text messages at quarterly intervals, reminding participants to get tested in a clinic. Participants in the standard HBST condition will receive their HBST in the mail when it is time for their quarterly tests. All study participants will have access to information that may be generally helpful (e.g., information about HIV, testing, and a testing clinic locator) and are already publicly available. Throughout the study, all participants will complete online questionnaires assessing key outcomes each quarter, which will be confirmed by reviewing clinical records in each local area when possible. Analyses will assess eTEST's efficacy within and across regions, as well as the cost-effectiveness of these strategies compared with relying on clinic-based testing alone.

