#### **B.4 Design and Methods**

In the study phase, 2000 high-risk MSM who have not tested in the last year will be recruited from three metro areas, Providence/Boston, Jackson, MS, and Los Angeles, CA, using ads on MSM-oriented, geolocation-based mobile “hookup” apps. They will be randomized to receive one of the following at three month intervals over the course of a year: (1) HBST with remote monitoring and post-test phone counseling/referral (eTEST condition), (2) standard HBST without active follow-up, or (3) reminders to get tested for HIV at a local clinic, delivered via text messages (control condition). We chose a three month retesting interval (HBST/reminder) to align with the CDCs most stringent recommendations for high-risk MSM98. During the study period, participants will complete quarterly surveys online. At 12 months, participants will be asked to present to a local clinic to provide a blood sample for HIV testing, to facilitate exploratory analyses comparing the number of infections successfully detected in each group and the “time to diagnosis” in each condition (see 3C.3.5.2 for more detail).

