## Planned Analyses

Analyses will be conducted in Year 5. To evaluate Aim 1(a), we will use factorial logistic regression to test whether rates of having completed any HIV test over the 12 month study period (assessed via self-report and/or clinic records) differ by study condition. Condition, study site (and their interaction) and other relevant covariates will be entered as predictors, allowing us to explore whether each condition's effects differ by study site. To explore the effects of study condition on regular HIV testing, we will use a generalized estimating equation (GEE) for repeated, binary outcomes, specifying whether participants tested during each 3-month study period as the focal outcome. A logit link function and independent correlation structure will be specified, with study condition, site, and relevant covariates as predictors, to test whether the odds of testing differ across time period, condition, and site. GEEs are a fitting approach for studies in which correlations between repeated measures variables are to be controlled, rather than a central focus of the analysis. For all models of **HIV testing** outcomes, a covariate reflecting whether a given participant had initiated PrEP (and when, for longitudinal models) will be added to each model, since these individuals are required to test for HIV quarterly as a part of ongoing PrEP care. Doing so will allow us to estimate the effects of study arm on HIV testing among those who did not initiate PrEP. Given that we have proposed collecting 54 more participants per site (162 total) than is required to estimate our most complex model (see Model 1b in Section 3C.3.10), we believe we will be fully powered to test this model, even with a high rate of PrEP adoption. While contamination of the control group in our pilot study was rare (only one control participant reported using a HBST), we will also track **where** each participant tested (at home, in person) in quarterly surveys. If contamination is significant, we will employ methods aimed at reducing this bias, including adding indicators of contamination as covariates or bootstrapping. To evaluate Aim 1(b), we will generate variables reflecting whether participants received testing for other STIs or risk reduction counseling during each of the four 3-month intervals of the study period. Similar GEE models will be estimated for these outcomes with time period, condition, and site as predictors, to test whether the odds of receiving each service differ across these factors. To evaluate Aim 2, we will code variables indicating whether participant reports or clinic records reflect participants having consulted with a medical provider about PrEP and/or received a PrEP prescription any time across the study period. Factorial logistic regression with study site, condition, and their interaction will be entered as predictors of this outcome, to test whether the odds of having received consultation and/or a PrEP prescription differ across each of the study sites and conditions. Overall, data from those who drop out or withdraw from the study will be used in these analyses, in intent-to-treat (ITT) fashion. Similarly, we will assume values of zero for all outcomes (i.e., non-receipt of testing or services) when quarterly assessments are missing but participants are retained in the study. Depending on the degree of missing assessments, we will use multiple imputation for these values, since data from missing assessments will likely be missing not at random.

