## B.5 Human Subjects Involvement, Characteristics, and Design

Participants will be 2000 males who are 18 years of age or older, not currently on PrEP and who have not received an HIV test in the last year. Focusing recruitment toward these individuals will allow us to examine whether the eTEST system and HBST increase testing and receipt of additional prevention services among those who rarely test and may be more difficult to reach with traditional prevention resources (i.e., clinic-based testing). Eligible participants will also report any of the following in the past 6 months: (1) anal sex (receptive or insertive) without condoms outside of a monogamous partnership with a recently tested, HIV-negative male, (2) having been diagnosed with an STI, or (3) having anal sex with an HIV-positive male. This criterion will ensure that the research is conducted among MSM who are at high risk for HIV and who meet DHHS criteria for pre-exposure prophylaxis. Since the research involves receiving HBST kits by mail, eligible participants will also be required to have a secure and stable residence to minimize the potential that tests may be stolen or diverted. This criterion was informed by past qualitative studies suggesting that most high-risk MSM prefer to receive tests by mail, as opposed to other delivery avenues (e.g., vending machine, pharmacy pickup). However, future research should address methods for providing “active” follow-up after HBSTs that are delivered via other routes, since many at highest risk may not have stable residences. Next, to be eligible, participants must currently have an Android or iOS smartphone with a data plan or a wifi internet connection at home. This ensures that the eTEST app can detect HBST kit openings when participants use the test at home. Finally, eligible participants will also be required to be fluent in either English or Spanish. All research materials will be translated into Spanish, and at least one test counselor and the LA site research assistant will be fluent in Spanish. These steps will ensure that we can explore the program’s effects specifically among Spanish-speaking Hispanic and Latino MSM. No special or vulnerable populations, as defined by 45 CFR Part 46 (e.g., prisoners, pregnant women, fetuses) are involved.

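### The power section justifies 300 participants per site, and the analysis section relies on the resulting surplus of 54, but enrolment is set at 2000 (666 per metro)

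*Combined protocol and SAP*

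**What the plan says.** Enrolment is stated in three places. The Overview of Research in B.1 has "High-risk MSM ( $N=2000$ , $N=666$ per metro) who have not tested in the last year". The opening of B.4 has "2000 high-risk MSM who have not tested in the last year will be recruited from three metro areas", and B.5 has "Participants will be 2000 males who are 18 years of age or older". The three metros are Jackson, Los Angeles and Providence/Boston.

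The sample-size argument is in Power Considerations, near the end of B.4. It assumes alpha 0.05, power 0.80, a site effect of 1.2 and, for the GEE models, four quarterly measurements with correlation 0.2. It says that the GEE sample sizes are the numbers needed to test condition effects within a site, gives 246 for the most demanding model, and closes: "To account for missing data, we propose collecting 300 MSM at each site".

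Planned Analyses, also in B.4, uses that margin when it discusses adjustment for PrEP initiation: "we have proposed collecting 54 more participants per site (162 total) than is required to estimate our most complex model". From this it concludes: "we believe we will be fully powered to test this model, even with a high rate of PrEP adoption".

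The Overview makes the general claim that "the proposed research involves conducting a fully-powered efficacy test of HBST", and plans to assess "efficacy within and across regions, as well as the cost-effectiveness of these strategies".

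**The concern.** Two paragraphs, on power and on analysis, describe a trial of 300 per site. Three others describe a trial of 2000. All of this is current running text. None of it comes from an amendment log, and rounding cannot bridge the gap.

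What is at stake is the basis of the full-power claim. It is made for the trial of 2000, but the only calculation offered stops at 300 per site. Someone judging the plan learns what 300 per site was meant to support. They do not learn what 2000 can detect, pooled or within a region, although both kinds of result are planned. The margin quoted in Planned Analyses is also not the margin of the trial whose enrolment is stated elsewhere. And the plan gives two answers on completion: recruitment of 900 would meet one target in full and the other at 45% (900/2000).

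**Working it through.** **Inputs**
- Required: 246 (Power Considerations), read as per site.
- Proposed to allow for missing data: 300 per site (Power Considerations).
- Surplus: 54 per site, 162 in total (Planned Analyses).
- Enrolment: 2000 (B.1, B.4, B.5); 666 per metro (B.1).
- Sites: 3.

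**1. Reproduce the plan's surplus**
- Per site: 300 − 246 = 54.
- Total: 3 × 54 = 162, or 3 × 300 − 3 × 246 = 900 − 738 = 162.

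Both match exactly. So 300 is not an isolated slip: Planned Analyses was written for three sites of 300, and the requirement was counted per site.

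**2. The same surplus at the stated enrolment**
- 3 × 666 = 1998, or about 2000.
- Per site: 666 − 246 = 420.
- Total: 3 × 420 = 1260 (counted from 2000: 2000 − 738 = 1262).

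**3. Size of the mismatch**
- Stated enrolment over justified size: 2000 / 900 = 2.22.
- Fraction a site could lose and still have 246: 1 − 246/300 = 18% at 300, and 1 − 246/666 = 63% at 666. The plan states no missing-data rate.
- For a fixed contrast, fixed rates and fixed allocation, standard errors scale with 1/√N. The ratio is √(300/666) = 0.67 within a site and √(900/2000) = 0.67 pooled. Detectable differences at the larger size are therefore about one third smaller than at the size the power section describes.

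**4. Can 246 itself be checked?**

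Not from the supplied text. Table 2, which is said to list the models, parameters and sample sizes, is absent. Its absence limits any check on 246, but it does not bear on the conflict between 300 and 666 per site.

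**The case against.** The strongest reply is that nothing is at risk. Three sections agree on 2000, and the Overview gives the matching 666 per metro. Only the power paragraph, and the sentence that draws on it, use the smaller figure. The natural reading is that those two were not updated when enrolment was raised. If 246 per site is enough, 666 is more than enough, and the claim of full power under high PrEP uptake becomes stronger. Effect sizes may also be set out in Table 2.

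Most of this stands. The documents favour 2000, although they never explain a move from 900, and the direction is safe. What remains is that the numbers offered in support belong to a different size of trial.

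Three stronger readings are tempting, and the documents do not support them.

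- *The trial is underpowered.* A reader might infer this from pilot figures. For repeat testing of 54% against 46% (B.1), two-sided alpha 0.05 and power 0.80, the two-proportion formula gives 613 per arm. Multiplying by the repeated-measures factor (1 + 3 × 0.2)/4 = 0.4 gives 245.2, rounded up to 246. If 246 were per arm within a site, a site would need 3 × 246 = 738, more than 666. With equal allocation (an assumption), within-site power would be about 43% at 300 per site and 76% at 666. But this is the only variant tried that lands on 246, and it may be coincidence. The text presents the figure per site, and the surplus of 54 is computed that way. Only Table 2 could settle it.
- *One cannot tell which size was justified.* One can: 300 per site was, and 2000 was not.
- *Using one margin for both missing data and PrEP uptake is an error in any case.* Planned Analyses keeps dropouts in the analysis and handles PrEP initiation with a covariate, so the two uses do not subtract one for one. The double use matters only if 300 per site is the real target.

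**Conclusion.** The text is wrong as written. The sample size in Power Considerations (300 per site, 900 in total) and the surplus in Planned Analyses (54 per site, 162 in total) do not match the stated enrolment of 2000 (666 per metro). At that enrolment the surplus over 246 would be 420 per site, about 1260 in total. No supplied passage gives power for 2000.

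No shortfall is shown and no power claim is shown to be false. The arithmetic rests on two assumptions: three sites of roughly equal size, and 246 being a per-site requirement. The first follows from 666 per metro and the second from the wording of the power paragraph. The value 246 is taken as given. The conflict between 300 and 666 does not depend on it.

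The point should be corrected because it concerns the headline design number and the only stated basis for the power claim. It does not by itself invalidate any planned analysis.

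**What to change.** State which enrolment figure is current, and bring the Overview of Research, the opening of B.4, B.5, Planned Analyses and Power Considerations into line with it.

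**If 2000 stands** (three sections support it):
1. Rerun the calculation at about 666 per site.
2. State power or detectable differences at that size, both pooled and within site.
3. Only then replace the surplus in Planned Analyses with the figure from the rerun. This is 420 per site, about 1260 in total, if 246 per site is confirmed.

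**If 300 per site is the target:** correct 2000 and 666 in B.1, B.4 and B.5. The margin of 54 should then not support both the missing-data allowance and the claim of full power under high PrEP uptake. State what each requires.

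The cost is text edits and one rerun of an existing calculation. If 2000 stands, enrolment does not change.
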